## APPENDIX 3. PATTERN MIXTURE MODEL WITH PLACEBO-BASED MULTIPLE

### IMPUTATION

- Step 1: In order to impute missing data for a given efficacy variable (e.g., PANSS total score), 500 datasets will be generated where missing data at intermediate visit(s) will be imputed based on non-missing data at baseline and all double-blind treatment period time points of the corresponding variable from all subjects within each treatment group using a multivariate normal distribution model and a Markov chain Monte Carlo (MCMC) imputation method. Country will be incorporated in the imputation model using dummy-coding of each classification level for the country by a binary (yes/no) variable. This imputation step will be implemented using the MCMC statement in the SAS® PROC MI procedure and the IMPUTE=MONOTONE option to obtain partial imputation where each imputed dataset will have intermittent missing values imputed, while monotone missing data will remain not imputed. An option to use multiple chains in the MCMC method will be used (option CHAIN=MULTIPLE in MCMC statement). Random number generator seed of 873465 will be used at this step.
- Step 2: For each dataset from Step 1, monotone missing data will be imputed based on information
  from the placebo group. As a result, 500 imputed complete datasets will be generated. This will be
  implemented by using SAS v9.4 PROC MI, statement MNAR MODEL (<variable to impute> /
  MODELOBS=(<treatment variable>='<placebo level>')). The imputation model will include baseline value
  and all post baseline time points prior to the one being imputed. Random number generator seed of
  12676854 will be used at this step.
- Change from Baseline to each post-Baseline time point will be computed based on observed and imputed data from Step 2. Each imputed complete dataset will be analysed with the same MMRM model as used for the primary analysis.
- Estimates obtained from the MMRM analysis applied to each imputed dataset will be combined using SAS MIANALYZE procedure.

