## 3. STUDY DESIGN

## **3.1. GENERAL DESCRIPTION**

This is a Phase 3, randomized, double-blind, placebo-controlled, in-patient, safety, and efficacy study to evaluate HP-3070 for the treatment of schizophrenia.

This study will consist of a Screening/placebo Run-in Period of 3 to 14 days, a 6-week double-blind Treatment Period and a 30 day Follow-up Period.

Subjects will be hospitalized at the Screening Visit and will remain hospitalized during the study. The subject may leave the hospital study for necessary personal business. Any subject who leaves the site must have an alcohol breathalyzer and urine drug tests when they return to the site.

After obtaining informed consent, each subject will be assigned a unique subject number. Eligible subjects will be hospitalized for the duration of the study. While undergoing screening procedures and waiting for results of laboratory tests, ECGs, and other assessments, the subject will start treatment with the single-blind placebo patch. The subject must have the single-blind placebo patch applied for a minimum of 3 days prior to being randomized into the double-blind Treatment Period. In addition, current antipsychotic and other prohibited medications will be washed out during the run-in period and must be completed prior to randomization into the double-blind treatment period. Details in regard to wash-out periods for specific drugs are summarized in Protocol Section 5.10.1. Subjects who have a decrease in PANSS total score ≥20% from Screening to Baseline or a PANSS total score <80 at Screening or Baseline will be discontinued from the study and will not enter the double-blind Treatment Period.

Document:	\\quintiles.net\Enterprise\Apps\sasdata\SASb\SAS\Noven\HP-			
Documenti	3070\XWA17541\Biostatistics\Docu	imentation\SAP\Final 6\Noven HP-3070-GL-04 S/	AP text Final	
	6_18Jan2018.docx			
Author:	[name]	Version Number:	Final 6	
		Version Date:	18Jan2018	
Template No:	CS TP BS016 – Revision 3	Reference: C	CS WI BS005	

Effective Date: 01May2012

Copyright © 2012 Quintiles Transnational Corp. All rights reserved.

Noven Pharmaceuticals, Inc. STATISTICAL ANALYSIS PLAN: PROTOCOL HP-3070-GL-04 Page 12 of 50

Subjects eligible for randomization into the double-blind Treatment Period will be randomly assigned to HP-3070 9.0 mg, HP-3070 18.0 mg, or placebo in a 1:1:1 ratio stratified by country. Subjects will receive treatment with study medication daily for 6 weeks.

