# 7.2. MULTICENTER STUDIES

This study will be conducted by multiple investigators at multiple centers internationally. Randomization to treatment arms will be stratified by country. Country will be used as a factor in statistical analyses.

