#### 15.3.3.2. Other Secondary Efficacy Endpoints Based on Binary (Responder) Variables

Effect of treatment on the proportion of PANSS responders from Baseline in PANSS total score as well as on the proportion of CGI-I responders at Weeks 1 through 6 will be tested using the Cochran Mantel Haenszel (CMH) method stratified by country. The hypothesis test will be based on the General Association statistic.

Descriptive summaries will be provided for the number and percentage of responders at Weeks 1 through 6 by treatment group. Also, estimates of the proportion of responders in each treatment group and differences of proportions (risk difference) between the treatment groups will be provided using the standard method based on the binomial distribution. Two-sided 95% CIs for proportion estimates based on the Wilson method and 2-sided 95% CIs for risk differences based on the Newcombe method will be reported.

#### 15.3.3.3. PANSS Continuous Responder Analysis at Week 6

A continuous responder analysis will be performed based on definition of responder at multiple levels of percent improvement from Baseline, from 5% to 100% with 5% increments. Results will be reported by means of a graph with response threshold on the X-axis and proportion of responders in each treatment group on the Y-axis. Corresponding data will be presented in a summary table.

Document:	\\quintiles.net\Enterprise\Apps\sasdata\SASb\SAS\Noven\HP-		
	3070\XWA17541\Biostatistics\Documentation\SAP\Final 6\Noven HP-3070-GL-04 SAP text Final		
	6_18Jan2018.docx		
Author:	[name]	Version Number:	Final 6
		Version Date:	18Jan2018
Template No:	CS TP BS016 – Revision 3	Reference: 0	CS WI BS005

Effective Date: 01May2012

Copyright © 2012 Quintiles Transnational Corp. All rights reserved.

Noven Pharmaceuticals, Inc. STATISTICAL ANALYSIS PLAN: PROTOCOL HP-3070-GL-04 Page 33 of 50

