## Table 14.2.1.2.3 Time-to-Failure Based on Change from Baseline in PANSS Total Score and Dropout Pattern 1Full Analysis Set

Statistic	HP-3070 18.0 mg (N=xxx)	HP-3070 9.0 mg (N=xxx)	Placebo (N=xxx)
Failures, n (%)	xx (x.xx)	xx (x.xx)	xx (x.xx)
Time to Failure (Days)			
25th Percentile	x.xx	X.XX	X.XX
Median	x.xx	X.XX	X.XX
75th Percentile	x.xx	x.xx	x.xx
Log Rank p-value	x.xxx	x.xxx	x.xxx
Probability of Failure at			
Week 1	X.XX	X.XX	X.XX
Week 2	X.XX	X.XX	X.XX
Week 3	X,XX	X.XX	X.XX
Week 4	X.XX	X.XX	X.XX
Week 5	X.XX	X.XX	X.XX
Week 6	X.XX	x.xx	x.xx

Note: PANSS = Positive and Negative Syndrome Scale, N = number of subjects in the full analysis set by treatment group.

Note: a subject is considered to have failed if there is never an improvement in PANSS score >=20% during the study or if there is an improvement >=20% during the study but a subsequent change from baseline <20%, or if the subjectdiscontinues for any reason. Note: Time to Failure is calculated based on Kaplan-Meier methodology.

Note: Percentages are calculated as (n/N)\*100.

Noven\HP-3070\XWA17541\Biostatistics\Production\Tables\xxxxx.sas ddmmmyyyy hh:mm

Author:

[name]

Version Number:

Version Date:

Draft 2 09Jan2017 Page 41 of 144

### Table 14.2.1.2.4 Time-to-Failure Analysis Based on Change from Baseline in PANSS Total Score and Dropout Pattern 2

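### Country, the only randomisation stratum, is missing from the placebo-based imputation step (Appendix 3, Step 2) and from the responder risk-difference intervals, although the matching analysis model and tests include it

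*SAP*

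**What the plan says.** **Design and primary model.** SAP section 3.1 assigns subjects to the two HP-3070 doses "or placebo in a 1:1:1 ratio stratified by country". No other stratification factor is given. Section 7.2 adds that "Country will be used as a factor in statistical analyses". The MMRM in section 15.1.3 has country as a class effect.

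**Placebo-based imputation (Appendix 3, for Scenario #1 of section 15.1.4).** Step 1 handles intermittent gaps: "Country will be incorporated in the imputation model using dummy-coding of each classification level for the country". Step 2 fills everything after discontinuation from placebo information. Its predictors are the baseline value "and all post baseline time points prior to the one being imputed", and country is not among them. Then: "Each imputed complete dataset will be analysed with the same MMRM model as used for the primary analysis". Section 15.2.3 carries the same analysis to CGI-S, the key secondary endpoint.

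**Responders (section 15.3.3.2).** CGI-I and PANSS responders are tested with a CMH general association statistic stratified by country. The proportions and their differences use the ordinary binomial method, and "2-sided 95% CIs for risk differences based on the Newcombe method will be reported" with no strata named. The footnotes to Tables 14.2.3.3 and 14.2.3.5 repeat this, naming country for the p-value only.

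**The concern.** Step 2 creates the values that make Scenario #1 differ from the primary analysis. Because country is named in Step 1 and absent from Step 2 of the same appendix, a programmer following the text would leave it out. Post-dropout values would then be drawn as though country told us nothing beyond the earlier scores, and would be analysed by a model that says it does. Subjects who leave early have few visits to carry their country's level, so they are affected most. At stake is the accuracy of one of the four sensitivity scenarios for the primary endpoint, and its CGI-S counterpart.

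For responders, a reader will see a p-value and an interval in the same column of one table. If country matters to response, the crude interval includes between-country variation that the stratified test removes. The two can then fall on opposite sides of significance.

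**Working it through.** **1. The plan's own figure.** For a difference of 7, SD 20, two-sided alpha 0.025 and 90% power, n = 2(2.2414 + 1.2816)² × (20/7)² = 202.6, so 203 per arm by the normal formula. The noncentral t gives 204 with power 0.900, as stated in section 3.1. Nothing here disputes that figure. The 7 points and 204 per arm are used below as yardsticks.

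**2. When the omission matters.** Let w_k be the share of country k, d_Ak and d_Pk the dropout proportions on active and placebo, and δ_k the part of the country effect that baseline and earlier visits do not carry. Without country in Step 2, each imputed value in country k misses δ_k. The Week 6 difference is then off by about

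−Σ w_k (d_Ak − d_Pk) δ_k.

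This is zero if dropout within each country is the same in both arms. It is close to zero if the arm difference in dropout is the same in every country. It is material only when dropout depends on arm and country together.

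**3. Simulation.** The SAP gives no country shares, country effects or dropout rates, so all are assumptions:
- Five countries, as in the Table 14.1.2 shell, with shares of 40, 30, 15, 8 and 7%.
- True on-treatment difference of −7 and Week 6 SD of 20.
- Country effects that grow over the six weeks.
- Sequential placebo-based regression imputation with and without country, then Week 6 regression on treatment, baseline and country. Very large samples were used, to isolate the systematic shift.

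Shift in the estimate (without country minus with country), in PANSS points:

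| Dropout pattern | Between-country SD 3 | SD 6 | SD 10 |
|---|---|---|---|
| 20% everywhere | −0.004 | −0.032 | −0.062 |
| Differs by country, same in both arms | −0.008 | −0.021 | −0.067 |
| Placebo 25%, active 15%, no country pattern | −0.006 | −0.017 | −0.058 |
| Differs by arm and country | +0.381 | +0.748 | +1.145 |

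In the last row placebo dropout is 35, 10, 10, 10, 10% across the five countries and active dropout is 10, 35, 25, 10, 10%. With country in the model the estimates are −6.11, −6.05 and −6.13. Without it they are −5.73, −5.30 and −4.99. Overall dropout is 20.0% on placebo and 19.75% on active, so a disposition table by arm alone would not reveal the pattern.

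*Hand check of the last row.* The country effects, scaled to SD 1, are 1.128, −1.195, −0.382, 0.199 and −0.731. Then −Σ w_k (d_Ak − d_Pk) × effect = 0.4×0.25×1.128 + 0.3×0.25×1.195 + 0.15×0.15×0.382 = 0.113 + 0.090 + 0.009 = 0.211 per unit of SD. At SD 6 that is 1.27 points if earlier visits carried nothing. The simulated 0.748 is 59% of this (60% at SD 3, 54% at SD 10), so earlier visits recover roughly 40 to 46% of the country effect.

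A separate simulation at 204 per arm used 1,500 trials per setting, country effects from −8 to +8 and about 25% dropout. It gave a shift of 0.1 to 0.15 points under even dropout. With active dropouts mainly from poorly responding countries and placebo dropouts the reverse, the shift was 0.7 to 1.2 points in the opposite direction: −7.0 to −7.1 without country against −5.8 to −6.3 with it. The sign depends only on which countries lose which patients.

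**4. Responder interval width.** The ratio of stratified to crude width is about √(mean within-country p(1−p) / pooled p(1−p)). Five equal-sized countries are assumed.
- Rates 25, 30, 35, 40, 45%: √(0.2225/0.2275) = 0.989, so the crude interval is 1/0.989 = 1.1% wider.
- Rates 15, 25, 35, 45, 55%: √(0.2075/0.2275) = 0.955, so the crude interval is 1/0.955 = 4.7% wider.

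**5. Test against interval.** 20,000 simulated trials per row, 204 per arm, the shares above, both at the two-sided 5% level:

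| Placebo response by country | Odds ratio | CMH p < 0.05 | Newcombe excludes 0 | Disagree |
|---|---|---|---|---|
| 20% in all | 1.00 | 4.98% | 4.96% | 0.03% |
| 20% in all | 1.72 | 64.6% | 64.8% | 0.24% |
| 12 to 30% | 1.00 | 5.03% | 4.71% | 0.33% |
| 12 to 30% | 1.72 | 65.0% | 63.6% | 1.4% |
| 6 to 50% | 1.00 | 4.88% | 3.48% | 1.4% |
| 6 to 50% | 1.72 | 61.4% | 53.7% | 7.7% |

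**The case against.** **Section 7.1 leaves the inclusion of covariates to each analysis section, so section 7.2 is not contradicted.** It is right that section 7.2 need not put country in every step. That does not settle the point, because the specific sections are where country drops out: in Appendix 3 between Step 1 and Step 2, and in section 15.3.3.2 between the test and its interval.

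**Step 2 already conditions on each subject's own history, and stratified randomisation balances country.** This stands, and it is why the shift is near zero in most patterns. A reader might infer that dropouts are simply pulled to an all-country placebo mean. They are not, since their earlier visits recover part of the country effect.

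**The larger shifts come from constructed dropout patterns.** This also stands. The SAP offers no evidence for or against joint arm-by-country dropout. A reader might infer that the omission flatters the drug, but the two simulations have opposite signs, so no direction can be claimed.

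**This is one sensitivity analysis among several.** Agreed. The SAP lists Scenario #1 with three others and ranks none above the rest. The rank ANCOVA in Appendix 4 also departs from missing at random and works within country.

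**The responder estimates are openly specified as crude, and the endpoints carry no multiplicity adjustment.** True. No confirmatory claim rests on them, and the cost is one of consistency and some width.

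**The log-rank test.** A reader might add that it is unstratified too. The documents do not say so. Section 15.1.4 names no test for time to failure, and the shell of Table 14.2.1.2.3 has only a row labelled "Log Rank p-value". That is missing detail, and no interval is attached to it. If it were run unstratified, simulation shows lost power and conservatism, not inflated type I error.

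**Conclusion.** Two omissions hold.

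1. The Step 2 imputation model leaves out a factor that the analysis model contains. The expected effect on the Week 6 difference is about 0.1 PANSS point or less in most settings. It can reach roughly 0.4 to 1.2 points, at most about one-sixth of the planned 7, if dropout depends on arm and country together and country effects are of the assumed size (between-country SD 3 to 10 points, or effects from −8 to +8). The direction cannot be known in advance.
2. The responder risk difference and its interval ignore the stratification used for their p-value. The interval is about 1% to 5% too wide under the assumed rates. Disagreement on significance is at most 0.24% of simulated trials without heterogeneity, 0.3 to 1.4% with moderate and 1.4 to 7.7% with strong heterogeneity. This applies only to the responder tables with a p-value, not to the continuous responder table.

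The primary MMRM and the sample size are unaffected, and no stated figure is wrong. This is a worthwhile, nearly free improvement and not a threat to the trial's conclusions.

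**What to change.** **Appendix 3, Step 2.** Add country, as a class variable, to the monotone regression used with the MNAR statement, so that it conditions on country, baseline and all earlier visits. State that this also applies to CGI-S.

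**Section 15.3.3.2 and the shells for the CGI-I and PANSS 30% responder tables.** Replace the crude difference with a country-stratified common risk difference and stratified Newcombe limits (COMMONRISKDIFF in PROC FREQ), and name country as the stratum in the footnote. The crude proportions per arm can stay as description. An occasional disagreement may remain because the test and interval are built differently, but the systematic cause goes.

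**Cost.** Two small code changes and a sentence for each. The drawback is sparse countries: Step 2 estimates the country terms from placebo subjects alone, so a small country may have few subjects to estimate from. A pooling rule should be fixed before unblinding, for example a minimum number of placebo subjects per country below which countries are merged along the regions already defined. If the sponsor prefers the unadjusted versions, the SAP should say so and give the reason.

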# APPENDIX 4. ANCOVA ON RANK-TRANSFPORMED DATA

ANCOVA on rank-transformed data to compare changes from baseline at a specific time point between treatment groups, adjusting for baseline and country, will be carried out based on the methodology described in Koch et al. (1982, 1990) and Stokes et al. (2012) as follows.

First the values of the change from baseline variable as well as baseline covariate will be transformed to standardized ranks within each country, using fractional ranks and mean method for ties:

proc rank nplus1 ties=mean out=RANKED\_DATA;

by <COUNTRY>;

var <BASELINE> <CHANGE\_FROM\_BASELINE>;

run;

Document: \\quintiles.net\Enterprise\Apps\sasdata\SASb\SAS\Noven\HP- 3070\XWA17541\Biostatistics\Documentation\SAP\Final 6\Noven HP-3070-GL-04 SAP text Final			AP text Final
Author:	6_18Jan2018.docx [name]	Version Number:	Final 6
		Version Date:	18Jan2018
Template No:	CS_TP_BS016 – Revision 3	Reference: C	CS WI BS005

Template No: CS\_TP\_BS016 – Revision 3 Effective Date: 01May2012

Copyright © 2012 Quintiles Transnational Corp. All rights reserved.

Then, separate regression models will be fit for each country using a regression model for change from baseline with baseline as predictor. Residuals from this regression model will be captured for further testing of differences between treatment groups:

proc reg DATA=<RANKED\_DATA>;

by <COUNTRY>;

model <CHANGE\_FROM\_BASELINE> = <BASELINE>;

output out=RESUDUALS r=RESID;

run;

Finally, the stratified (for country) Cochran-Mantel-Haenszel test based on the Row Mean Score Differ statistic using the values of the residuals as scores will be used to compare treatment groups in a pairwise fashion (including one HP-3070 dose group and placebo at a time):

proc freq DATA=RESIDUALS;

tables <COUNTRY> \* <TREATMENT> \* RESID / CMH2;

run;

Document:	\\quintiles.net\Enterprise\Apps\sas	sdata\SASb\SAS\Noven\HP-	
	3070\XWA17541\Biostatistics\Docu	umentation\SAP\Final 6\Noven HP-3070-GL-04 SA	AP text Final
	6_18Jan2018.docx		
Author:	[name]	Version Number:	Final 6
		Version Date:	18Jan2018
Template No: 0	CS_TP_BS016 – Revision 3	Reference: C	S_WI_BS005

Template No: CS\_TP\_BS016 – Revision 3 Effective Date: 01May2012

Copyright © 2012 Quintiles Transnational Corp. All rights reserved. The contents of this document are confidential and proprietary to Quintiles Transnational Corp. Unauthorized use, disclosure or reproduction is strictly prohibited.

# **MODIFICATION HISTORY**

Unique Identifier for this Version	Date of the Document Version	Author	Significant Changes from Previous Authorized Version
1.0 (SAP Draft V4)	06OCT2016	[name]	Not Applicable – First Version
2.0 (SAP	12JAN2018	[name]	Review Comments Implemented
Draft V5)			Key changes:
			Coordinated with SAP updates to reflect updated protocol
			Removed sensitivity for secondary efficacy
			Added disposition and demographic summaries from IVRS/IWRS
			Added additional information on screening to Analysis sets table
			Updated table formatting
			Removed disposition during run- in table
			Reorganized Analysis Sets, Disposition and Randomization Tables
			Added new figures by PANSS subscales
			Added table and listing for PK
			Updated skin irritation table to include combined and concatenated scores
			Updated presentation of region to North America, Russia and Rest of the World

Author:

[name]

Version Number: Version Date: Draft 2 18Jan2018 Shells Page **3** of **144** 

3.0 (SAP Draft V6)	18JAN2018	[name]	Removed ATC coding for concomitant medications
			Removed analysis using ITT population for primary efficacy variable
			Added sensitivity analysis for secondary efficacy variable

Author:

[name]

Version Number: Version Date: Draft 2 18Jan2018 Shells Page 4 of 144

### **OUTPUT CONVENTIONS**

General:

- The first row in the body of the table or listing should be blank
- The left hand column should start in column 1. No indenting or centering of the output should occur.
- Rounding should be done with the SAS function ROUND.
- Numbers in tables should be rounded, not truncated.
- Alphanumeric output should be left aligned.
- Numbers should be decimal point aligned.
- Whole numbers should be right aligned.
- Text values should be left aligned.
- The first letter of a text entry should be capitalized
- Listings of adverse events, concomitant medications, medical histories etc. should be sorted in chronological order, with earliest adverse event, medication or history coming first.
- All listing outputs should be sorted (preferably by Treatment, Site Number and Subject Number).
- Do not use superscripts and subscripts
- Exponentiation will be expressed using a double asterisk, i.e., mm3 will be written as mm\*\*3.

Univariate Statistics:

• Statistics should be presented in the same order across tables (i.e., n, Mean, SD, Median, Minimum, Maximum)

- Table statistics should line up under the N part of the (N=XXX) in the table header. All decimal points should line up. If the minimum and maximum are output on one line as Minimum, Maximum then the comma should line up with the decimal point.
- If the original data has N decimal places, then the summary statistics should have the following decimal places:

Minimum and maximum: N Mean, median and CV%: N + 1 SD: N + 2

Frequencies and percentages (n and %):

- Percent values should be reported inside parentheses, with one space between the count and the left parenthesis of the percentage. Parentheses should be justified to accept a maximum of 100.0 as a value and padded with blank space if the percent is less than 100.0. An example is given below: 77 (100.0)
  - 50 (64.9)

0(0.0)

Percentages will be reported to one decimal place, except percents <100.0% but >99.9% will be presented as '>99.9%' (e.g., 99.99% is presented as >99.9%); and percents < 0.1% will be presented as '<0.1%' (e.g., 0.08% is presented as <0.1%). Rounding will be applied after the <0.1% and >99.9% rule.

```
E.g. ( <0.1%)
( 6.8%)
(>99.9%)
```

Percentages may be reported to 0 decimal places as appropriate (for example, where the

Author:	[name]	Version Number:
		Version Date:

Draft 2 18Jan2018 Shells Page **12** of **144** 

denominator is relatively small).

• Where counts are zero, percentages of 0.0% should appear in the output.

Confidence Intervals:

- As a rule confidence intervals are output to one place more than the raw data, and standard deviations and standard errors to two places more than the raw data
- Confidence intervals should be justified so that parentheses displayed on consecutive lines of a table "line up".
- Boundary values of confidence intervals should be separated by a comma.
- Boundary values should be padded as necessary to accept negative values and to allow alignment of the decimal place.
- An example is given below: (-0.12, -0.10) ( 9.54, 12.91)

